Suprainguinal Fascia Iliaca (SIFI) Block Improves Analgesia Following Total Hip Arthroplasty

Document Date: December 11, 2019

NCT02933671

1. Protocol Title:

Suprainguinal Fascia Iliaca (SIFI) Block Improves Analgesia Following Total Hip Arthroplasty.

2. Purpose of the Study:

The goal of this prospective randomized double-blind study is to determine if an ultrasound guided suprainguinal fascia iliaca (SIFI) technique is efficacious as an analgesic for total hip arthroplasty. Efficacy will be determined by analyzing post-intervention pain scores (NRS 11), opioid consumption, and functional status including ambulation and dynamometry for quadriceps function. English speaking ASA 1-3 patients ages 18-75 years old undergoing primary total hip arthroplasty will be assessed post-operatively after a general anesthetic. Once pain scores are $>5/10$, patients will be blocked with either 0.2% ropivacaine or saline, and numerical pain scores and opioid consumption will be evaluated over the following 24 hours. Data will be analyzed on an intent to treat basis using a two-sided t-test (parametric) or Mann-Whitney-Wilcoxon (non-parametric) with a p-value of 0.05 as significant. Patients will assume standard risk associated with nerve blocks, including theoretical risk of nerve damage and local anesthetic systemic toxicity.

3. Background & Significance:

Several regional anesthesia techniques have been implemented to decrease postoperative pain following total hip arthroplasty (THA), with varying success^{1,2}. Of these, the fascia iliaca block is commonly utilized nerve block for hip surgery. This block anesthetizes the lateral femoral cutaneous nerve (LFCN), but has a reported 10-37% failure rate³⁻⁵. To reduce failure, the femoral nerve and the LFCN have been blocked individually utilizing ultrasound guidance. The LFCN, if blocked individually, has traditionally been approached below the inguinal ligament³⁻⁸ and has been shown to be useful in patients with chronic pain. In chronic pain, desired sensory block of the LFCN while avoiding motor block is important, leading to deposition of local anesthetic distal to the inguinal ligament.

Anterior approaches for total hip arthroplasty have led to careful cadaveric examination of the course of the LFCN⁹⁻¹¹ following reports of LFCN damage caused by the anterior approach^{8,9}. The LFCN has an unreliable course with variable branching below the inguinal ligament. The branching is variable such that one or more branches may course above, through, or below the inguinal ligament. The branches may cross *sartorius* laterally anywhere from 0-9 cm below the inguinal crease⁹⁻¹¹. In contrast, the LFCN has a reliable course above the inguinal ligament and conserved course superficial to *iliacus* muscle and immediately below the fascia iliaca in the pelvis⁸.

Swenson, *et al.*¹², described injection of local anesthetic under the fascia iliaca at the level of the inguinal ligament with subsequent distal compression to advance the local anesthetic in a retrocaudal direction with MRI confirmation of distribution using dye. Sensory deficit in the distribution of the LFCN was demonstrated in all patients although local anesthetic was up to 2.2 cm laterally from the ASIS in 40% of their subjects. This technique, however, causes a significant motor block since local anesthetic is injected near the femoral nerve.

Hebbard, *et al.*¹³, described an infrainguinal approach for suprainguinal needle placement in cadavers and demonstrated dye surrounding LFCN in the pelvis by advancing the needle in a cephalad direction underneath the inguinal ligament¹³. Despite the potential advantages of the suprainguinal needle placement, the long needle entry path and difficulty imaging the correct fascial plane, particularly in obese patients, can

make this approach challenging. As such, this approach has not been widely studied in the several years since its description.

Similarly, Kumar, *et al.*¹⁴, described a modified suprainguinal approach using a landmark based technique during which the needle was placed 1 cm above the inguinal ligament and 1/3 of the distance medially from the ASIS to the pubic tubercle. With this technique, decreased VAS pain scores were seen, as was less morphine consumption and less post-operative nausea and vomiting than patients receiving traditional infrainguinal fascia iliaca blocks, showing a benefit for suprainguinal injection.

Our recent case series comprised of 5 patients described the novel ultrasound guided out-of-plane suprainguinal fascia iliaca (SIFI) plane block¹⁵. The approach described requires new probe positioning and new sonographic landmarks for combined LFCN and femoral nerve analgesic block. Pain scores were slightly lower in the block group, however, opioid consumption was decreased. Gross motor function was preserved despite local anesthetic tracking down to femoral nerve, however no qualitative measures were taken. Overall, the ultrasound guided SIFI approach to anesthetizing the LFCN showed promise, but has not been adequately evaluated for efficacy in a prospective study.

4. Design & Procedures:

Preoperatively, patients will be given standard of care premedications: 975mg acetaminophen and 300mg gabapentin by mouth prior to surgery. These medications may be altered or not given depending on patient comorbidities or other extenuating factors such as allergy/intolerance. Furthermore, a spinal anesthetic will be placed in the preoperative area.

Patients will be taken to the operating room and sedated using IV propofol to a bispectral index (BIS) of 60-80, indicating adequate sedation. Once sedated, patients will be given a 0.5mg/kg ketamine bolus (based on ideal body weight) and 10mg dexamethasone will be given prior to incision. The orthopedic surgery attending will determine the degree of preoperative knee extension prior to the procedure and inform the anesthesia team. At conclusion of the case sedation will be stopped and patient will be taken to the post-operative care unit (PACU).

Post-operatively study interventions will begin. Patients will be assessed from arrival in PACU to determine their level of pain as well as nausea/vomiting. Once the patient reported pain score in the recovery area is $\geq 5/10$ on a 0-10 numerical pain scale study personnel will initiate intervention. Patients will be given a one time IV bolus of 15mg ketorolac.

Patients will be randomized into either SIFI block or sham group with an online randomization program by the study PI ([name]) prior to any patient enrollment. Patients will be given a number (1-40), and the randomized numbers will be given to key study personnel member that will be unblinded. The intervention drug, either 30mL 0.2% ropivacaine or sham block, consisting of 30mL saline, will be drawn up by this key personnel member of the study team who is unblinded and will not be involved in the SIFI block or post-operative analysis. This person will supply the regional anesthesiologist with the intervention, however, both the regional anesthesiologist performing the block and the patient will be blind as to the contents of the syringe.

At the completion of the intervention, verbally reported pain scores (NRS 11) and opioid consumption (IV morphine equivalents) will be measured by a blinded observer starting at time zero and monitored every 10 minutes for 1 hour (+/- 5 minutes). Verbal pain scores will then be recorded each hour for first 4 hours, 6 hours and 24 hours (+/- 10 minutes). Patients will have post-operative orders for supplementary pain control that

include 25mcg IV fentanyl for pain scores 5-7 and 50mcg IV fentanyl for pain scores 8-10.

Subjects' verbal pain scores and opioid consumption will be recorded hourly for the first four hours, at 6 hours, and at 24 hours. Dynamometry will be utilized 2 hours post intervention on POD0 to determine the extent of quadriceps weakness achieved by SIFI injection as compared to unblocked leg. Ambulation distance in feet will be measured POD0 and POD1 by physical therapy. These results will be recorded as will hospital length of stay.

5. Selection of Subjects:

ASA 1-3 patients aged 18-75 years old undergoing primary hip arthroplasty will be enrolled. Patients will be identified preoperatively in either preoperative screening clinic or the night prior to surgery depending on method of preoperative screening. Patients in the study will be ASA 1-3 patients, many will be screened by phone instead of a clinic visit. Patients not seen in preoperative screening clinic will be contacted by telephone by primary investigator ([name]) to confirm eligibility and, if eligible and interested, the study will be explained. Patients will be given the opportunity to ask initial questions about the study over the phone. Patients interested in participating will be again have the protocol fully explained and written informed consent will be obtained on the day of surgery prior to receiving any sedation

Inclusion

Patients that will be included in the study are English speaking 18-75 year old ASA 1-3 patients undergoing primary total hip arthroplasty.

Exclusion

Patients will be excluded from the study if they meet one or more of the following Criteria:

- 1) ASA 4 or 5
- 2) Revision hip arthroplasty
- 3) Diagnosis of chronic pain
- 4) Daily chronic opioid use (over 3 months of continuous opioid use).
- 5) Inability to communicate pain scores or need for analgesia.
- 6) Acute hip fracture
- 7) Infection at the site of block placement
- 8) Age under 18 years old or greater than 75 years old
- 9) Pregnant women (as determined by standard of care day-of surgery urine bHCG)
- 10) Intolerance/allergy to local anesthetics
- 11) Weight <50 kg
- 12) Suspected or known addiction to or abuse of illicit drug(s), prescription medicine(s), or alcohol within the past 2 years.
- 13) Uncontrolled anxiety, schizophrenia, or other psychiatric disorder that, in the opinion of the investigator, may interfere with study assessments or compliance.
- 14) Current or historical evidence of any clinically significant disease or condition that, in the opinion of the investigator, may increase the risk of surgery or complicate the subject's postoperative course.

6. Subject Recruitment & Compensation:

Only patients who are having total hip arthroplasty are eligible for this study. We will not bias any demographic groups in identifying patients eligible for this study. A total of 40 patients will be consented from Duke University Medical Center. An IRB approved phone script may be used to discuss the study with eligible patients missed at their Pre-Op screening visit. Patients will not receive any additional compensation for enrollment in this study.

7. Consent Process

A patient's permission to be approached for research will be obtained by the primary care team involved with the patient. The consent process will be conducted by the research personnel or one of the physicians involved in the study. The consent process will take place in the pre-operative screening or the surgical clinics. Throughout the consent process, measures will be taken to maintain privacy, such as by conducting face-to-face conversations in private rooms. As much time as necessary will be spent with each potential subject to sufficiently explain and answer all questions, and address all concerns they may have in regard to the study and/or consent process. Under HIPAA waiver, the study team will identify potential subjects from clinic schedules, OR schedules and Maestro Care.

8. Subject's Capacity to Give Legally Effective Consent:

Patients who do not have the capacity to give legally effective consent will not be approached for participation in this study.

9. Study Interventions:

See 4 above.

10. Risk/Benefit Assessment:

Patients will not incur any added risk to standard risks incurred with regional anesthesia. These standards risks are:

- Regional anesthesia - minor pain or discomfort, injury to arteries, veins or nerves affecting the arms or legs, residual numbness or weakness or paralysis, headache, muscle soreness, infection, allergy or adverse drug reaction, intravascular injection of local anesthetic causing seizure or cardiac arrest.

Patients will be monitored in the post-operative care unit by nurses assigned to their care. Once pain scores ≥ 5 , the study team will be notified and the intervention will be performed. Patients will have post-operative analgesics available for pain control that include 25mcg IV fentanyl for pain scores 5-7 and 50mcg IV fentanyl for pain scores 8-10. Fentanyl will not be administered prior to intervention unless intervention cannot be performed within 5 minutes of notification by PACU nurse.

Benefits include contributing to general knowledge base to improve future patient care. This includes potential confirmation of analgesic benefit, decreased pain scores, and improved patient satisfaction. Conversely, this study may show no benefit of the block, thereby invalidating the technique.

11. Costs to the Subject:

Subjects will not incur any additional costs to participate in the study. A MaestroCare build will be created to ensure that any subjects are not charged for researched related procedures, equipment, or medications.

12. Data Analysis & Statistical Considerations:

The primary hypothesis, that there is a difference in numeric pain score at 4 hours postoperatively between the intervention groups, will be assessed with a two-sided 2 group t-test or Mann-Whitney-Wilcoxon test as appropriate. We will perform a secondary repeated measures ANOVA or non-parametric Friedman test to assess difference in numeric pain score over the full 24-hour period. If there is evidence of a difference in numeric pain score during the 24-hour period, we will perform post-hoc pair-wise multiple comparison corrected tests to identify the time-points where the intervention groups differ on pain score. Additional secondary analyses will assess differences in cumulative opioid consumption in IV morphine equivalents and motor strength for both tibial and common peroneal nerves with parametric or non-parametric tests as appropriate. Statisticians employed by the Department of Anesthesiology will conduct these analyses.

A total of 40 participants will be enrolled in the study, randomized equally between study (n=20) and placebo (n=20) groups based on sample size calculation for a non-parametric Mann-Whitney Test with $\alpha=0.05$, $\beta=0.8$, difference in means=2, and effect size of 1.0. The sample size required for a non-parametric test will provide greater than 80% power if the data meet requirements for a parametric t-test.

13. Data & Safety Monitoring:

In accordance with federal regulations the PI will monitor for, review, and promptly report to the IRB, appropriate institutional officials, sponsor, coordinating center and the appropriate regulatory agency head all unanticipated problems involving risks to subjects or others that occur in the course of a subject's participation in a research study (45 CFR 46.103(b)(5)(i) and 21 CFR 56.108(b)(1)), all AE reports will be reported per the DUHS IRB policies. PI will be monitoring all AEs and submitting reports to the IRB per DUHS IRB policy.

14. Privacy, Data Storage & Confidentiality

Potential subjects and their families will be approached private rooms. Any guests not involved in the consent process will be asked to leave the room during any such communications, unless the patient allows them to be present. Efforts to maintain subject confidentiality will include following Federal Privacy Regulations which provide safeguards for privacy, security, and authorized access. Except when required by law, subjects will not be identified by name, social security number, address, telephone number, or any other direct personal identifier in study records disclosed outside of Duke University Health System (DUHS). Subjects will not be revealed in any reports or publications resulting from this study. For records disclosed outside of DUHS, subjects will be assigned a unique code number. The paper and electronic data will be stored as per the RDSP.

REFERENCES:

3. Foss NB, Kristensen BB, Bundgaard M, et al. Fascia Iliaca Compartment Blockade for Acute Pain Control in Hip Fracture Patients. *Anesthesiology*.

2007;(106):773-778.

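### Allocation concealment is not assured: the PI generates the whole list before enrolment, apparently also screens by phone, and no safeguard is written down

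*Combined protocol and SAP*

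**What the plan says.** **Generation and custody (Section 4, Design & Procedures).** "Patients will be randomized into either SIFI block or sham group with an online randomization program by the study PI", and this happens before any enrolment. "Patients will be given a number (1-40), and the randomized numbers will be given to key study personnel member that will be unblinded". That team member draws up the syringe and is described as someone "who is unblinded and will not be involved in the SIFI block or post-operative analysis".

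**Blinding (Section 4).** "both the regional anesthesiologist performing the block and the patient will be blind as to the contents of the syringe". The observer who records pain scores and opioid use is also blinded.

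**Screening (Section 5, Selection of Subjects).** "Patients not seen in preoperative screening clinic will be contacted by telephone by primary investigator" to confirm eligibility and hear the study explained. The section adds that "many will be screened by phone instead of a clinic visit". Exclusion 13 covers psychiatric disorders that "in the opinion of the investigator, may interfere with study assessments or compliance". Exclusion 14, on clinically significant disease, also depends on the investigator's opinion.

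**Consent (Sections 5 and 7).** Section 5 says that "written informed consent will be obtained on the day of surgery prior to receiving any sedation". Section 7 lets research personnel or any study physician conduct the consent process, after the primary care team has obtained the patient's permission to be approached.

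**The concern.** Concealment and blinding are separate protections. Concealment keeps those who decide on entry from knowing the next assignment. Blinding acts after entry. The roles that Section 4 names as blind are the patient, the block operator and the observer. The PI is not named, and none of these provisions operates at the telephone call or at consent.

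If a person who screens or consents can foresee an assignment, candidates can be accepted, discouraged or excluded according to the arm they would enter. A comparison of the 4-hour pain scores would then include differences in who was admitted, and a blinded syringe does not remove them. With 20 patients per arm, selective entry could not be ruled out afterwards. Uncontrolled anxiety (exclusion 13) and conditions that may complicate the postoperative course (exclusion 14) are matters of judgement that could plausibly relate to reported pain.

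**Working it through.** **1. The plan's own figure.** Section 12 gives 40 patients (20 per arm) for a Mann-Whitney test with alpha 0.05, difference 2 and effect size 1.0. It prints beta as 0.8, read here as power. The exact two-sided t-test needs 16.71 per arm. Dividing by the minimum relative efficiency of the Mann-Whitney test, 16.71 / 0.864 = 19.35, which rounds up to 20 per arm and 40 in total. The figure reproduces, and the concealment point does not depend on it. The implied SD is 2 / 1.0 = 2 NRS points.

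**2. The text, step by step.**

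| Question | What the plan gives | What it leaves open |
|---|---|---|
| Who makes the list, and when? | The study PI, before enrolment (Section 4) | Whether the PI sees or keeps it |
| Who receives it? | One unblinded preparer (Section 4) | Whether it is handed over unseen |
| What is the preparer barred from? | The block and post-operative analysis (Section 4) | Screening and consent |
| Who screens by phone? | The primary investigator (Section 5) | Whether this is the same person as the study PI (names removed) |
| Who takes consent? | Research personnel or a study physician (Section 7) | Whether the PI or the preparer may do so |
| When is a number attached to a patient? | Not stated | Timing and order |

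The plan mentions no sealed envelopes, no independent holder of the list, and no release of single assignments after consent.

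**3. What steering would require.** (a) A person who screens or consents knows the list. (b) That person can tell which number the candidate will receive. (c) That person has discretion to act on it. The text leaves (a) and (b) open. Exclusions 13 and 14 and the telephone explanation supply some scope for (c).

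**4. Illustration of size.** The documents give no input for this, so all three are assumed:
- f: share of patients phoned by the PI. Section 5 says only that there are many, so 10% to 100% is shown.
- q: share of phoned candidates selectively rejected, in opposite directions by arm.
- r: correlation of the predictor used for rejection with the pain score, set at 0.3.

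The shift among phoned patients, in SD units, is s = 2 × r × φ(z_q) / (1 − q). For q = 10%: 2 × 0.3 × 0.1755 / 0.90 = 0.117. For q = 20%: 2 × 0.3 × 0.2800 / 0.80 = 0.210. For q = 24.5%: 2 × 0.3 × 0.3144 / 0.755 = 0.25.

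The whole-trial shift is f × s. The chance of p < 0.05 with no true effect comes from the noncentral t with 38 degrees of freedom and noncentrality f × s × √(20/2):

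| q | f = 10% | f = 25% | f = 50% | f = 100% |
|---|---|---|---|---|
| 10% | 5.01% | 5.09% | 5.37% | 6.50% |
| 20% | 5.05% | 5.30% | 6.21% | 9.92% |
| 24.5% | 5.07% | 5.43% | 6.72% | 12.02% |

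Simulating the selection itself (100,000 trials per cell) at f = 25% and 50% gave 5.0% and 5.4%, 5.4% and 6.2%, and 5.5% and 6.7% for the three rows.

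In NRS points the shift is f × s × 2. It runs from 0.10 × 0.117 × 2 = 0.02 to 1.00 × 0.25 × 2 = 0.50, against a planned difference of 2. The model assumes that requirements (a) and (b) are fully met for every phoned patient. If either is not met, the rate stays at 5%.

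**The case against.** The strongest reply is that this is a gap in documentation and not a demonstrated defect. No text says that the PI views or keeps the list. An online program may or may not display it. Passing the numbers to one designated person suggests that others are not meant to hold them. That the study PI and the primary investigator are one person is an inference from the role. Steering from a phone call also requires knowing which number the candidate will get. After the call come written consent on the day of surgery and a pain threshold in recovery before the intervention. If numbers are attached only at that threshold, a phone screener could not reliably match a candidate to an arm. Most exclusions are factual, clinic patients are not phoned by the PI, and the primary care team's permission comes first.

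All of this stands as a limit on the concern. A reader might infer that concealment was broken or that the result is biased, and the documents do not support that. These features narrow the opportunity, but none of them conceals the list. Because the timing of numbering is unstated, the plan cannot rely on late assignment as a protection. If the two investigator roles belong to different people, the gaps over the preparer and the numbering order remain.

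A further objection is that the error-rate figures are too small and too dependent on assumptions to carry the point. That is accepted: the point rests on the role assignment and the missing safeguards. It might also be said that a sentence stating that the list passes unseen would be enough. It would narrow the gap, but moving generation away from a person who apparently screens costs about the same and does not depend on an assurance.

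**Conclusion.** The point holds as a weakness that should be fixed, with medium confidence. The plan expressly gives generation of the complete list to the PI before enrolment, apparently gives the same person telephone eligibility decisions, and describes no concealment from those who screen or consent.

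The conclusion rests on two things: the reading that both titles denote one person, and the absence of any stated safeguard. It does not rest on a size. The range of about 5.0% to 12.0% is conditional on assumed f, q and r and on numbers being predictable at screening. The upper end needs every patient to be phoned and about a quarter of candidates to be rejected by arm, so it must not be read as the trial's actual error rate.

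**What to change.** Amend Section 4 as follows.

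- **Generation.** Replace generation by the study PI with generation by an existing staff member who has no role in screening, consent, block, outcome assessment or outcome analysis. A departmental statistician is suitable only if that person does not analyse this trial, because Section 12 assigns the analyses to the departmental statisticians.
- **Custody.** The generator gives the list only to the unblinded syringe preparer. Bar the preparer from screening and consent, in addition to the block and the analysis.
- **Assignment.** Assign numbers in strict sequence, only after eligibility and written consent are final. Release each assignment only at syringe preparation.
- **Access.** The PI and anyone who screens, consents, assesses or analyses has no access to the list until database lock, except for unblinding of an individual patient for safety.

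The cost is a few sentences and a small shift of duties among existing staff. No patients are added, and N stays at 40.

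### Section 12 does not adjust the primary 4-hour pain comparison for pre-block pain; pre-specifying that adjustment is a cheap, probably modest gain in efficiency, not the repair of an error.

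*Combined protocol and SAP*

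**What the plan says.** Section 12 states the primary hypothesis as whether "there is a difference in numeric pain score at 4 hours postoperatively between the intervention groups", and says that it "will be assessed with a two-sided 2 group t-test or Mann-Whitney-Wilcoxon test as appropriate". Section 2 fixes the two-sided level, "with a p-value of 0.05 as significant", and calls for analysis by intention to treat. No covariate is named for the primary or any secondary analysis, and no reason is given for leaving baseline pain out.

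Section 4 has pain assessed from arrival in the PACU. When the score reaches 5 out of 10, "study personnel will initiate intervention"; Section 10 repeats this trigger. So each treated patient has a pain score that precedes the randomised injection. The scheduled study scores begin later: after the block is complete, pain and opioid use "will be measured by a blinded observer starting at time zero and monitored every 10 minutes for 1 hour".

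The sample size in Section 12 rests on "difference in means=2, and effect size of 1.0", with patients "randomized equally between study (n=20) and placebo (n=20) groups".

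**The concern.** A pain score taken before the randomised injection cannot be affected by it, and the patient and the anaesthesiologist doing the block are blinded to the syringe contents. It is therefore a legitimate baseline covariate. If it predicts 4-hour pain, an unadjusted comparison leaves explainable variation in the error term. With 20 per arm, the confidence interval is then wider than it needs to be, and a chance difference in starting pain goes unaddressed by any planned analysis. Adjustment chosen only after an imbalance has been seen would be hard to defend, so the decision belongs in Section 12 now.

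**Working it through.** **Inputs.** From the documents: two-sided alpha 0.05, 20 per arm, difference 2, effect size 1.0. The implied SD is 2/1.0 = 2.0. Section 12 prints 0.8 as beta; it is read here as power, because the next sentence says that the sample size "will provide greater than 80% power if the data meet requirements for a parametric t-test". Assumed, because the documents give no value: rho, the within-arm correlation between pre-block and 4-hour NRS.

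**The plan's own figure.** By the noncentral t distribution with effect size 1.0, power is 78.1% at 16 per arm and 80.7% at 17, so a t-test needs 17. Dividing by 0.864, the minimum asymptotic relative efficiency of the Mann-Whitney test, gives 17/0.864 = 19.7, rounded up to 20 per arm. The stated size is reproduced.

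**Unadjusted power at 20 per arm.** SE = 2 × sqrt(2/20) = 0.632; noncentrality = 2/0.632 = 3.16 on 38 df; power 86.9%. For the Mann-Whitney test it is 85.3% under normality and 81.4% at minimum efficiency.

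**ANCOVA power at 20 per arm.** Relative variance = (1 - rho²) × (1 + 1/36). The second factor allows for chance imbalance in the covariate. Noncentrality = 3.16/sqrt(relative variance), on 37 df.

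| assumed rho | relative variance | power, SD 2 | power, SD 2.5 (assumed) |
|---|---|---|---|
| unadjusted | 1.00 | 86.9% | 69.3% |
| 0 | 1.03 | 85.9% | 68.1% |
| 0.2 | 0.99 | 87.3% | 69.9% |
| 0.3 | 0.94 | 89.0% | 72.2% |
| 0.4 | 0.86 | 91.2% | 75.5% |
| 0.5 | 0.77 | 93.9% | 80.1% |

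Variance breaks even where (1 - rho²) × 37/36 = 1, that is rho = sqrt(1/37) = 0.16.

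**Effect of the trigger.** Only scores of 5-10 lead to a block, so the covariate has a restricted spread. Let k be the ratio of restricted to unrestricted SD, and R the unrestricted correlation. Then rho = R × k / sqrt(1 - R² + R² × k²). If unrestricted pre-block pain had mean 4-6 and SD 2-2.5 (assumed), k is about 0.55 to 0.70.

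- R = 0.3 falls to between 0.17 and 0.21.
- R = 0.5 falls to between 0.30 and 0.37.

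Over rho 0.17 to 0.37, the gain at SD 2 is about 0 to 3.5 power points, and the variance falls by roughly 0 to 11%.

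**Check with bounded integer scores.** In a simulation of 4,000 trials per setting, baseline was rounded and confined to 5-10 (assumed latent mean 6.5, SD 1.3), and 4-hour scores to 0-10 (assumed latent mean 5 in the control arm, SD 2, difference 2). Here rho is the latent correlation.

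| latent rho | t-test | Mann-Whitney | ANCOVA |
|---|---|---|---|
| 0 | 86.1% | 84.7% | 85.0% |
| 0.2 | 85.6% | 84.2% | 85.8% |
| 0.3 | 86.4% | 84.5% | 87.8% |
| 0.5 | 86.3% | 84.4% | 92.1% |

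The pattern matches the formula: little at rho 0.2, and a clear gain only at the higher values.

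**Chance imbalance.** With an assumed baseline SD of 1.5, the SE of the baseline difference is 1.5 × sqrt(2/20) = 0.474, and a gap of at least 0.5 points has probability about 29%. At an assumed SD of 1.0 it is about 11%. The gap reaches the 4-hour difference only through the regression slope, rho × 2/1.5. A 0.5-point gap therefore moves the result by 0.5 × 0.3 × 2/1.5 = 0.20 points at rho 0.3, and by 0.33 at rho 0.5, against a planned difference of 2.

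**The case against.** The strongest reply is that nothing here is broken. Randomisation makes the unadjusted test valid, and its p-value already allows for chance imbalance. Its power exceeds 80% on the plan's inputs, and the rank option needs no linear model for a bounded integer score. All of that stands.

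The benefit also depends wholly on an unknown correlation. The trigger truncates the covariate, scores may cluster near 5, and ketorolac at the time of the block and later fentanyl may weaken the link with 4-hour pain. Below rho of about 0.16, ANCOVA does slightly worse. This stands too, and it limits the size that can be claimed.

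Two practical objections shape the fix. Allocation is generated before enrolment and analysis is by intention to treat, so a randomised patient who never reaches the trigger has no trigger score. And Section 10 allows fentanyl before the block if the block is delayed beyond 5 minutes, so the trigger score and the last score before the block need not be the same.

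A reader might infer that the trial already records the baseline score, so that only the analysis text need change. The documents do not say so: they show that the score is obtained, while scheduled recording starts once the block is complete. A reader might also infer that chance imbalance passes in full into the 4-hour result; the slope calculation shows that it does not.

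**Conclusion.** The point holds as a low-cost efficiency improvement. The primary analysis is unadjusted, a valid pre-treatment score is obtained in every treated patient, and no reason is given for not using it. At SD 2 the effect on power runs from a loss of about 1 point at rho 0 to a gain of about 7 at rho 0.5, with about 0 to 3.5 points the more realistic range once truncation is allowed for. The direction is secure above rho of about 0.16. The size is not, because rho, the baseline spread and the effect of the trigger are all assumptions. It would go too far to conclude that the trial is underpowered or the planned test wrong: on the stated inputs it is neither.

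**What to change.** - **Section 4:** record the last NRS before the block as a study variable. Do not use the time-zero score as the covariate, since it is taken after the injection.
- **Section 12:** pre-specify, as the primary analysis, an ANCOVA of the 4-hour NRS on treatment and that pre-block score. Report the adjusted mean difference with its 95% confidence interval. Keep the unadjusted Mann-Whitney test as a sensitivity analysis, which preserves a check that does not rely on a linear model.
- **Section 12:** state how randomised patients who never reach the trigger are handled, for example by using their last recorded PACU score as the covariate.
- **Sections 2, 4 and 10:** the trigger is given as above 5 in Section 2 and as 5 or more in Sections 4 and 10. These must be reconciled, because they set the range of the covariate.

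The cost is one extra data field, a few sentences and one degree of freedom, with no extra patients. The downside is about 1 power point if pre-block pain turns out not to predict 4-hour pain.
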